5.5 Rule of exclusion criteria of analysis sets

The following protocol deviations will be considered as major and will lead to exclusion of subjects from the respective analysis set:

Protocol Deviation ID (DVSPID)	Decription used to Report PDs to HA/IRBs (DVTERM)	Population	Severity code
INCL01	Written informed consent is not obtained before assessment is performed	Excluded from PPS	4
INCL02	Age less than 18 years and greater than 80 years.	-Excluded from PPS if Age < 18 years -Included in both FAS & PPS if Age > 80 years	4 0
INCL04	Not diagnosed with Heart Failure NYHA class II or III	Excluded from PPS	4
INCL05	Not diagnosis of Heart Failure with reduced Ejection Fraction (LVEF lessthan 40%) and NYHA class II or III	Excluded from PPS	4
INCL06	Unstable to any dose of ACEI or ARB prior to enrolment in the study	Excluded from PPS only if patient is NOT on any dose of ACEI or ARB	4
INCL07	Unstable to any dose of a beta-blocker prior to enrolment in the study	Excluded from PPS only if patient is	4

		NOT on any dose of Beta-Blocker	
INCL08	Not Eligible for treatment with LCZ696 (ENTRESTOTM) as per Canadian product monograph	Excluded from PPS	4
INCL09	Not Treated as an outpatient	Excluded from PPS	4
INCL10	Informed consent is not signed on agreeing to participate in the study	Excluded from, PPS, SAF and FAS	4, 3
EXCL01A	Symptomatic hypotension at Baseline	Excluded from PPS	4
EXCL01B	SBP less than 100 mmHg at baseline visit	Excluded from PPS	4
EXCL02	Estimated GFR lessthan 30 mL/min/1.73m2 as measured by the simplified Modification of Diet in Renal Disease (MDRD) formula at baseline visit.	Excluded from PPS	4
EXCL03	Known history of angioedema related to previous ACEI or ARBs therapy, or history of hereditary or idiopathic angioedema.	Excluded from PPS	4
EXCL04	Requirement of concomitant treatment with both ACEIs and ARBs	Excluded from PPS	4
EXCL05	Concurrent participation in other clinical trials or receiving other investigational drugs within 30 days of enrollment.	Excluded from PPS	4
EXCL06	Hypersensitivity to the active substances, sacubitril or valsartan, or to any of the excipients.	Excluded from PPS	4
EXCL07	Concomitant use of aliskiren- containing drugs in patients with diabetes mellitus (type 1 or type 2) or moderate to severe renal impairment (GFR lessthan 60ml/min/1.73m2).	Excluded from PPS	4
EXCL08	History of hypersensitivity to any of the study drugs or to drugs of similar chemical classes.	Excluded from PPS	4
EXCL09	History of malignancy of organ system (other than local basal cell carcinoma of skin), treated or untreated, within the past 5 years, regardless there is evidence	Excluded from PPS	4
EXCL10	Pregnant or nursing (lactating) women, where pregnancy is defined as the state of a female after conception and until the termination of gestation, confirmed by a positive hCG laboratory test.	Excluded from PPS	4

EXCL11	Women of childbearing potential, defined as all women physiologically capable of becoming pregnant, unless they are using effective methods of contraception during dosing of study treatment	Excluded from PPS	4
WITH01	Patient become pregnant, while taking study medication.	Excluded from PPS	0
WITH02	Due to the potential risk of angioedema when used concomitantly with an ACEI, LCZ696 is started within 36 hours without discontinuation of ACEI therapy.	Excluded from PPS	4
OTH01	Pregnancy test not performed as required per protocol	Excluded from PPS	0
OTH02	Pregnancy not reported within 24 hrs to Novartis while patient is on study treatment	Excluded from PPS	4
OTH03	Approved ICF update available but patient has not signed this version		
TRT01	Treatment with ARBs is not discontinued prior to intiation of study treatment	Excluded from PPS	4

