	
 
To describe the impact of LCZ696 on functional exercise capacity, as measured by the Six Minute Walk Test, at 6 and 12 months.
 
To describe the time of up-titration for each dose (24 mg sacubitril / 26 mg valsartan and 49 mgsacubitril / 51 mg valsartan bid ) of LCZ696.
 

	• To describe the adherence to guideline recommended dosing of beta-blockers and MRAs at 6 and 12 months of treatment with LCZ696.
	To evaluate the overall safety profile of LCZ696 during 12 months of treatment

Study Design	This will be a multi-center, open label, prospective post- approval (phase IV) study. Patients with HFrEF that are eligible to be treated with LCZ696 as per the ENTRESTO TM product monograph will be enrolled in the study. The study patients will be enrolled at Canadian community cardiologists and IM specialists sites that treat patients with HFrEF. Follow up will be for 12 months, with the primary endpoint being assessed at 6 months of treatment.
	The patients will continue on their background treatment with the exception of ACEIs and ARBs that will be replaced with LCZ696, as per recent guidelines, after a 36 hour wash-out period for ACEIs. All patients will be initiated on the lower dose of LCZ696 as per the product monograph and the treating physician's judgement. A starting dose of 24 mg sacubitril / 26 mg valsartan twice daily may be considered in selected patients, for example, those on less than guideline-recommended doses of ACEI or ARB prior to initiation of LCZ696. The dose of LCZ696 should be increased every 2-4 weeks, as tolerated by the patient and in accordance to the product monograph, to the target dose of 97 mg sacubitril / 103 mg valsartan twice daily. If patients experience tolerability issues, e.g. symptomatic hypotension or hyperkalemia, consideration should be given to temporary down-titration of LCZ696 (as per ENTRESTO TM Canadian product monograph). Dose reduction of other concomitant medications including nitrates, CCBs, alpha- blockers and diuretics may be considered to optimize the tolerability of treatment with LCZ696.
Population	The target population of the study will be patients with HFrEF that are candidates for treatment with LCZ696 as per the Canadian product monograph.
Inclusion Criteria	
 
Age ≥ 18 years and ≤ 80 years.
 
Males or females.
 
Diagnosis of Heart Failure with reduced Ejection Fraction (LVEF ≤ 40%) and NYHA class II or III.
 

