## 4.1 Inclusion criteria

Patients eligible for inclusion in this study have to fulfill **all** of the following criteria:

- 1. Written informed consent must be obtained before any assessment is performed.
- 2. Age  $\geq$  18 years and  $\leq$  80 years.
- 3. Males or females.
- 4. Diagnosis of Heart Failure NYHA class II-III.
- 5. Diagnosis of Heart Failure with reduced Ejection Fraction (LVEF  $\leq 40\%$ ) and NYHA class II or III.
- 6. Stable on any dose of ACEI or ARB prior to enrolment in the study
- 7. Stable on any dose of a beta-blocker prior to enrolment in the study.
- 8. Eligible for treatment with LCZ696 (ENTRESTOTM) as per Canadian product monograph.
- 9. Treated as an outpatient.
- 10. Signed an informed consent agreeing to participate in the study.

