2.15 Interim analysis

An interim analysis may be performed after 50 patients have reached 12 weeks of treatment, and at any

time during the study as long as it does not impact the study completion.

3 Sample size calculation

The primary outcome measure for the current study will be the proportion of patients on 97 mg sacubitril / 103 mg valsartan bid of LCZ696 at 6 months of treatment. The data from clinical trials have shown that at 12 weeks (3 months) approximately 80% of patients have achieved this dose. In this current real – life study of 6 months (primary endpoint) a reasonable estimate of patients achieving this dose would be 70%.

Given that this is a single cohort, prospective study in which all patients are receiving the same treatment and the objective is to describe the proportion of patients reaching 97 mg sacubitril / 103 mg valsartan bid LCZ696, sample size requirements are based on the precision of the estimate. This is assessed with the 95% confidence interval. A reasonable level of precision is one with a 95% confidence interval width (ω) that is between 5 and 15% of the point estimate. With 300 patients enrolled in the study, the 95% Confidence Interval width will be \pm 5.2% which is equivalent to 7.4% of the point estimate of 70%, with upper and lower limits of 64.8% – 75.2% respectively. This is within the limits of reasonable precision.

4 Change to protocol specified analyses

Not applicable.

5 Appendix

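### SAP deviation INCL05 is written against LVEF below 40%, but the protocol admits 40% or less, so an eligible patient at exactly 40% would be dropped from the per-protocol set

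*SAP*

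**What the plan says.** The protocol synopsis sets the criterion as "Diagnosis of Heart Failure with reduced Ejection Fraction (LVEF ≤ 40%) and NYHA class II or III". Inclusion criterion 5 in protocol section 4.1, which opens "Diagnosis of Heart Failure with reduced Ejection Fraction", carries the same limit: LVEF of 40% or less together with NYHA class II or III.

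SAP section 5.5 introduces its table with "The following protocol deviations will be considered as major and will lead to exclusion of subjects from the respective analysis set". The description for INCL05 is "Not diagnosis of Heart Failure with reduced Ejection Fraction (LVEF lessthan 40%) and NYHA class II or III". Its population entry is exclusion from the PPS, without qualification, and its severity code is 4.

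SAP section 2.2 bases the primary analysis on the FAS, defined as everyone who received at least one dose, and sets the safety set equal to the FAS. It defines the PPS by completion of the 6- and 12-month assessments and does not mention LVEF. The LVEF limit therefore acts on the PPS only through section 5.5.

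**The concern.** An analysis-set rule should remove patients who broke the protocol, not patients who met it. INCL05 replaces a limit that includes 40% with one that leaves it out, so a patient at exactly 40% satisfies criterion 5 and still fits the description of a major deviation.

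Two things are at stake. First, the PPS is used. SAP section 2.2 plans analyses in both the FAS and the PPS unless otherwise specified, SAP section 2.5.4 makes the PPS the sensitivity analysis for the primary endpoint under a stated condition, and protocol section 9.4.6 uses per-protocol patients to test the assumption made for patients lost to follow-up. Second, the column that holds the wording is the text used to report deviations to health authorities and review boards. As it stands, it gives them a limit that differs from the approved protocol.

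**Working it through.** **Step 1: the two rules side by side.** The protocol rule is eligible if LVEF ≤ 40 (synopsis; section 4.1, criterion 5). INCL05 as written is a deviation if not LVEF < 40, that is, if LVEF ≥ 40 (SAP section 5.5). With NYHA class II or III in every case:

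| LVEF | Protocol | INCL05 as written | Agree? |
|---|---|---|---|
| 39% | eligible | no deviation | yes |
| 40% | eligible | deviation, out of PPS | **no** |
| 41% | not eligible | deviation, out of PPS | yes |

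The rules differ at the single value 40%.

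**Step 2: is the word meant strictly?** The table spells the comparison out in letters, so a symbol lost in text extraction does not explain it. EXCL02 in the same table reads "Estimated GFR lessthan 30 mL/min/1.73m2 as measured by the simplified Modification of Diet in Renal Disease (MDRD) formula at baseline visit", and the matching protocol exclusion is a strict < 30. EXCL07 uses the word in the same way for GFR below 60. The consistent reading in this table is strict.

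**Step 3: is it a declared change?** Where the table relaxes a protocol criterion, it says so in the population column. INCL02 has "Included in both FAS & PPS if Age > 80 years", and INCL06 and INCL07 carry their own conditions. INCL05 has none. The SAP section headed "4 Change to protocol specified analyses" is answered as not applicable. No other SAP text restores the 40% limit.

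**Step 4: size.** The plan's own precision figure (protocol section 9.6, SAP section 3) reproduces: 1.96 × √(0.70 × 0.30 / 300) = 0.0519, so ± 5.2%, 64.8% to 75.2%, and 0.0519 / 0.70 = 7.4% of the estimate. It refers to 300 patients and is not altered by INCL05.

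The number removed from the PPS is 300 × s, where s is the share at exactly 40%. The documents do not give s. As an illustration only, with s assumed, the other patients all in the PPS, and a proportion of 70%:

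- s = 2%: 6 removed; half-width 1.96 × √(0.21 / 294) = 5.24%.
- s = 15%: 45 removed; half-width 1.96 × √(0.21 / 255) = 5.62%.

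These values show how precision responds. They do not estimate what will happen.

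**Step 5: after correction.** If the deviation is not LVEF ≤ 40, then 39% and 40% are not deviations and 41% is. The rule then removes no patient who meets the LVEF criterion.

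**The case against.** The strongest reply is that the wording sits in a reporting label. The lead-in speaks of protocol deviations, and a patient at 40% has none to classify. The entry carries the number of criterion 5, and other labels in the table are loose too: INCL02 describes an age both below 18 and above 80, which no patient can have, and EXCL11 restates the criterion instead of its breach. If sites flag deviations against the protocol text, a patient at 40% may never be flagged. This stands as a reason to think the wording is a slip in transcription, and it means that actual removal is possible but not certain. It does not remove the point: the label is also the only statement of the condition that the population column acts on, and a programmer working from ejection fraction, which SAP section 2.3.2 summarises at baseline, could apply it literally.

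A reader might infer more than the documents support, in four ways:

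- *That the primary result is compromised.* It is not; it rests on the FAS.
- *That many patients, say 15 to 45 of 300, would be lost.* This needs an assumed share of 5% to 15% at exactly 40%, and neither document supplies one.
- *That the error alone would set off the 10% condition for repeating analyses in the PPS.* This needs more than 30 of 300 at exactly 40%, and it assumes that the undefined difference between the FAS and PPS samples means sample size. Non-completers also leave the PPS, so the condition might be met anyway. Section 2.2 also plans PPS analyses generally.
- *That the mildest patients are removed.* The plan does not grade severity by LVEF, and a patient at 40% may be in NYHA class III. Only the highest eligible LVEF value can be claimed.

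**Conclusion.** The point holds as a contradiction between the protocol and the SAP at one value. Applied as written, INCL05 records a protocol-eligible patient with LVEF of exactly 40% as a major deviation and removes that patient from the PPS. This conclusion rests on the text of the two documents alone, on reading the word strictly as elsewhere in the table, and on literal application of the entry. The number affected is unknown and may be small. The FAS primary estimate, its confidence interval and the safety set are unchanged. The matter deserves correction because it is a wrong threshold in a rule that decides membership of an analysis set; it does not put the main conclusion in doubt.

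**What to change.** Reword INCL05 to mirror inclusion criterion 5, for example: *Does not have a diagnosis of HFrEF with LVEF less than or equal to 40% and NYHA class II or III.* On LVEF, only values above 40% are then deviations. Keep the joint form. Replacing the entry with LVEF greater than 40% alone would drop the NYHA part of the criterion, and would miss a patient with no qualifying diagnosis or LVEF on record.

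Make the same change in the deviation specification, and check that no patient at exactly 40% has been coded under INCL05. The cost is one line in the SAP, one in the specification, and a short data check. Nothing in the protocol needs to change.

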5.6 Adverse event of special interest

For reporting of AESIs, document "AEs of special interest preferred terms" will be used.

Document received for Medical Lead will be placed in CREDI as it is.

5.7 Target dose of cardiovascular medication

For reporting of targed dose of beta blockers and MRAs, document "Canadian drugs for HFrEF" will be used. Document received for Medical Lead will be placed in CREDI as it is.

6 Reference

Protocol has been used as a reference.
